***If clinically indicated tissue from a biopsy will also be banked using the UCCCC# 8980 banking protocol.***

**2. -- 2 Purple top tubes, blood volume, processing etc will follow HTRC SOPs**

**3. – PAXgene tube, blood volume, processing etc will follow HTRC SOPs**

**\* Treatment cycle length = 21 days**

**\*\* After cycle 8, as clinically appropriate ECOG performance status, physical exam, and adverse event recording interval may be increased to every other cycle (=every 6 weeks).**

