## 5.3 Dose Modifications

Adverse events (both non-serious and serious) associated with pembrolizumab and epacadostat exposure may represent an immunologic etiology. These adverse events may occur shortly after the first dose or several months after the last dose of treatment. Pembrolizumab must be withheld for drug-related toxicities and severe or life-threatening AEs as per Table 3 below. See below for supportive care guidelines, including use of corticosteroids.

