**Table 3: Dose Modification Guidelines for Drug-Related Adverse Events for Pembrolizumab and Epacadostat**

Toxicity	Hold Treatment For Grade	Agent	Timing for Restarting Treatment	Dose Level for	Treatment Discontinuation
Diarrhea/Colitis	2-3	Pembrolizumab	Toxicity resolves to Grade 0-1	n/a	Toxicity does not resolve within 12 weeks of last dose or inability to reduce corticosteroid to 10 mg or less of prednisone or equivalent per day within 12 weeks

		Epacadostat	Toxicity resolves to Grade 0-1	Related: Reduce by 1 dose level Not Related: Same dose level	Toxicity does not resolve within 12 weeks of last dose or inability to reduce corticosteroid to 10 mg or less of prednisone or equivalent per day within 12 weeks
	4	Pembrolizu mab	Permanently discontinue	n/a	Permanently discontinue
		Epacadostat	Permanently discontinue	n/a	Permanently discontinue
AST, ALT, or Increased Bilirubin	2	Pembrolizu mab	Toxicity resolves to Grade 0-1	n/a	Toxicity does not resolve within 12 weeks of
		Epacadostat	Toxicity resolves to Grade 0-1	Related: Reduce by 1 dose level Not Related: Same dose level	Toxicity does not resolve within 12 weeks of last dose
	3-4	Pembrolizu mab	Permanently discontinue	n/a	Permanently discontinue
		Epacadostat	Permanently discontinue	n/a	Permanently discontinue
Type 1 diabetes mellitus (if new onset) or Hyperglycemia	T1DM or 3-4	Pembrolizu mab	Hold pembrolizumab for new onset Type 1 diabetes mellitus or Grade 3-4 hyperglycemia associated with evidence of beta cell failure	n/a	Resume pembrolizumab when subjects are clinically and metabolically stable
		Epacadostat	Toxicity resolves to Grade 0-1	Related: Reduce by 1 dose level Not Related: Same dose level	Resume epacadostat when subjects are clinically and metabolically stable

Dosing interruptions are permitted in the case of medical / surgical events or logistical reasons not related to study therapy (e.g., elective surgery, unrelated medical events, patient vacation, and/or holidays). Subjects should be placed back on study therapy within 3 weeks of the scheduled interruption, unless otherwise discussed with the PI. The reason for interruption should be documented in the patient's study record.

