#### **Table 4: General Approach to Handling Immune-Related Adverse Events**

irAE	Withhold/Discontinue Pembrolizumab (MK-3475) and Epacadostat	Supportive Care
Grade 1	No action.	Provide symptomatic treatment.
Grade 2	May withhold MK-3475 and INCB024360. Subjects with intolerable or persistent Grade 2 drug-related AE may hold study medication at physician's discretion. Permanently discontinue study drug for persistent Grade 2 AEs for which treatment with study drug has been held, that do not recover to Grade 0 to 1 within 12 weeks of the last dose.	Consider systemic corticosteroids in addition to appropriate symptomatic treatment.
Grade 3 or severe	Withhold MK-3475 and INCB024360. Discontinue if unable to reduce corticosteroid dose to < 10 mg/day prednisone equivalent within 12 weeks of toxicity or permanently discontinue for any severe or ≥ Grade 3 drug-related AE that recurs or any life-threatening event.  For grade 3 rash, dose interruption and topical treatment (see next column) until resolution are recommended. Resume at same dose although dose reduction in cases of persistent rash can be considered.	Systemic corticosteroids are indicated in addition to appropriate symptomatic treatment.  Topical steroids per physician choice (e.g. hydrocortisone, or stronger). Typically oral steroids are not required.
Grade 4	Permanently discontinue	Systemic corticosteroids are indicated in addition to appropriate symptomatic treatment.

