### **5.3.6 Timing of Dose Administration of Pembrolizumab.**

Combination treatment (during treatment period) should be administered on Day 1 of each cycle after all procedures/assessments have been completed as detailed on the Trial Flow Chart (Section 6.0). Trial treatment may be administered up to 3 days before or after the scheduled Day 1 of each cycle due to administrative reasons.

→ All trial treatments will be administered on an outpatient basis.

Pembrolizumab 200 mg will be administered as a 30-minute IV infusion every 3 weeks until disease progression, unacceptable toxicity, or up to 24 months in patients without disease progression. . Sites should make every effort to target infusion timing to be as close to 30 minutes as possible. However, given the variability of infusion pumps from site to site, a window of -5 minutes and +10 minutes is permitted (i.e., infusion time is 30 minutes: -5 min/+10 min).

The Pharmacy Manual contains specific instructions for the preparation of the pembrolizumab infusion fluid and administration of infusion solution.

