## 6.0 TRIAL FLOW CHART

### 6.1 Study Flow Chart

Trial Period:	Screening Phase		Treatment Cycles *								End of Treatment (D/C)	Post-Treatment			
	Treatment Cycle/Title:	Pre-screening (Visit 1)	Main Study Screening (Visit 2)	1	2	3	4	To be repeated beyond 8 cycles **				Safety Follow-up	Follow Up Visits	Survival Follow-Up	
Scheduling Window (Days):		-28 to -1		± 3	± 3	± 3	± 3	± 3	± 3	± 3	± 3	At time of D/C	30 days post D/C	Every 8 weeks post D/C	Every 12 weeks
Administrative Procedures															
Informed Consent	X														
Inclusion/Exclusion Criteria	X	X													
Demographics and Medical History	X	X													
Prior and Concomitant Medication Review	X	X	X	X	X	X	X	X	X	X	X	X			
Trial Treatment Administration			X	X	X	X	X	X	X	X	X				
Post-study anticancer therapy status												X			
Survival Status												X	X	X	X
Clinical Procedures/Assessments															
Epacadostat administration (daily po)			X	X	X	X	X	X	X	X	X				
Pembrolizumab administration (iv q3 weeks)			X	X	X	X	X	X	X	X	X				
Review Adverse Events			X	X	X	X	X	X**	X	X**	X				
Full Physical Examination		X	X	X	X	X	X	X**	X	X**	X	X	X	X	
Vital Signs and Weight		X	X	X	X	X	X	X	X	X	X	X	X	X	
ECOG Performance Status		X	X	X	X	X	X	X**	X	X**	X	X	X	X	

Trial Period:	Screening Phase		Treatment Cycles*								End of Treatment	Post-Treatment			
	Treatment Cycle/Title:	Pre-screening (Visit 1)	Main Study Screening (Visit 2)	1	2	3	4	To be repeated beyond 8 cycles**				Discontinuation (D/C)	Safety Follow-up	Follow Up Visits	Survival Follow-Up
							5	6	7	8					
Scheduling Window (Days):		-28 to -1		± 3	± 3	± 3	± 3	± 3	± 3	± 3	± 3	At time of D/C	30 days post D/C	Every 8 weeks post D/C	Every 12 weeks
feasible															
Correlative Studies Blood Collection including a) germline DNA collection and b) PAXgene tube for RNA		X 		X 											

**1. The fresh biopsy/FNA requirement can be waived under extenuating circumstances after approval by the PI ([name]) e.g such a procedure is not safe or technically feasible.**

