### **7.1.2 Clinical Procedures/Assessments**

#### **7.1.2.1 Adverse Event (AE) Monitoring**

The investigator or qualified designee will assess each subject to evaluate for potential new or worsening AEs as specified in the Trial Flow Chart and more frequently if clinically indicated. Adverse experiences will be graded and recorded throughout the study and during the follow-up period according to NCI CTCAE Version 4.0. Toxicities will be characterized in terms regarding seriousness, causality, toxicity grading, and action taken with regard to trial treatment.

Please refer to section 7.2 for detailed information regarding the assessment and recording of AEs.

Safety assessments will consist of monitoring and recording all adverse events and serious adverse events, the regular monitoring of hematology, blood chemistry and urine values, regular measurement of vital signs and the performance of physical examinations.

These assessments should be performed within  $\pm 7$  days of the scheduled day of assessment except for adverse events that will be evaluated continuously through the study. Safety and tolerability will be assessed according to the NIH/NCI CTC [http://evs.nci.nih.gov/ftp1/CTCAE/CTCAE\\_4.03\\_2010-06-14\\_QuickReference\\_5x7.pdf](http://evs.nci.nih.gov/ftp1/CTCAE/CTCAE_4.03_2010-06-14_QuickReference_5x7.pdf)

Patients whose treatment is interrupted or permanently discontinued due to an adverse event or abnormal laboratory value suspected to be related to treatment must be followed at least weekly until the adverse event or abnormal laboratory resolves or returns to grade 1. If a patient requires a dose delay of >16 weeks from the intended day of the next scheduled dose, then the patient must be discontinued from the study.

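### After cycle 8 the Flow Chart allows scheduled adverse event review every 6 weeks while pembrolizumab stays every 3 weeks, so about half of the later infusions may have no scheduled symptom check beforehand

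*Combined protocol and SAP*

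**What the plan says.** The note to the Section 6.1 Flow Chart sets a 21-day cycle and, for the cycles beyond the eighth, says: "as clinically appropriate ECOG performance status, physical exam, and adverse event recording interval may be increased to every other cycle (=every 6 weeks". In the chart, the double asterisk appears on the row "Review Adverse Events" at cycles 6 and 8 of the block that repeats beyond cycle 8. It also appears on the physical examination and ECOG rows. The row "Pembrolizumab administration (iv q3 weeks" has no such mark, nor do the vital signs and medication review rows.

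Three body sections bear on whether a review is still due before each infusion:

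- Section 7.1.2.1: the site physician or a delegate "will assess each subject to evaluate for potential new or worsening AEs as specified in the Trial Flow Chart and more frequently if clinically indicated". The same section exempts AEs from the ±7 day assessment window because they are to be evaluated continuously.
- Section 5.3.6: treatment "should be administered on Day 1 of each cycle after all procedures/assessments have been completed as detailed on the Trial Flow Chart".
- Section 7.1.2.4: ECOG is assessed before each dose, but as the Flow Chart specifies.

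The hold rules are firm. Section 5.3 says "Pembrolizumab must be withheld for drug-related toxicities and severe or life-threatening AEs as per Table 3 below". Table 3 holds both drugs for Grade 2-3 diarrhea/colitis, and the restart condition for each is "Toxicity resolves to Grade 0-1". Table 4 withholds both drugs for Grade 3 immune-related events and adds: "For grade 3 rash, dose interruption and topical treatment (see next column) until resolution are recommended".

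**The concern.** A mandatory hold works at a given dose only if someone knows the patient's toxicity status before that dose. Diarrhea, colitis and rash are found largely by asking and looking. Vital signs and blood tests do not reliably show them. The diarrhea/colitis hold begins at Grade 2, which Table 8 describes as moderate; hospitalization is mentioned only from Grade 3. A hold-level event may therefore not come to light through serious AE reporting.

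Section 5.7.1 calls for oral corticosteroids once Grade 2 diarrhea/colitis has lasted more than 3 days, and Section 5.3 warns that immune-related events can appear late. Epacadostat is taken at home twice daily, so a skipped review can also delay its hold. Under the note, AE review, physical examination and ECOG can all drop out of the same infusion visit.

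There is a lesser consequence for the safety objective. Section 8.1 tabulates toxicities by type and severity, and less frequent scheduled questioning makes that record somewhat less complete.

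**Working it through.** **The plan's own figure.** Two cycles × 21 days = 42 days = 6 weeks, as the note states.

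**When the option starts.** Cycle 9 begins on day 8 × 21 + 1 = 169, after 24 full weeks. On the chart's pattern (marks on even cycles) the first skipped review is cycle 10, day 9 × 21 + 1 = 190. If cycle 9 is skipped instead, it is day 169.

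**Gap between scheduled reviews.** The nominal gap is 42 days instead of 21. With the ±3 day dosing window at both ends, the longest gap is 42 + 3 + 3 = 48 days, against 21 + 3 + 3 = 27. At two epacadostat doses a day, the nominal gap spans 42 × 2 = 84 doses instead of 21 × 2 = 42. This measures dosing between reviews, not undetected toxicity.

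**Infusions without a scheduled AE review, if the option is used throughout with no dose delays.** The documents give two treatment limits, so both are shown.

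- *18 administrations (Section 5.9).* Cycles 9-18 are 10 infusions. Skipping even cycles 10-18 or odd cycles 9-17 gives 5 of 10 (50%), or 5 of 18 overall (28%).
- *24 months (Section 5.3.6), taken as 104 weeks.* 104 × 7 = 728 days and 728 / 21 = 34.7, so there are 35 cycle starts. Cycles 9-35 are 27 infusions. Skipping even cycles 10-34 gives 13 of 27 (48%; 13 of 35 overall, 37%). Skipping odd cycles 9-35 gives 14 of 27 (52%; 14 of 35 overall, 40%).

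**Does other text restore the review at a skipped visit?**

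- *Section 5.3.6* makes dosing wait for the procedures in the Flow Chart. If the chart does not call for AE review at that visit, nothing is outstanding.
- *Section 7.1.2.1* follows the chart, with more frequent assessment only if indicated. Its continuous-evaluation clause is a real duty but fixes no contact before a dose.
- *Section 7.1.2.4* puts ECOG before each dose but defers to the chart, where the ECOG row carries the same mark. ECOG is also not a toxicity inquiry.
- *Section 7.3* records AEs at each examination, and the examination is itself relaxed.
- *Sections 5.3.2 and 10.9* (prompt discussion of Grade 2 or higher immune-related events; real-time AE entry) operate once an event is known.
- *Sections 7.1.2.3 and 7.2.7* keep vital signs and acceptable laboratory results before each dose, and the chart keeps medication review at each cycle. These are genuine pre-dose checks, but not a symptom review.

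No sentence in the available text schedules an AE or symptom review before each infusion after cycle 8.

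**The case against.** The strongest reply is that the plan already covers this. A duty to evaluate AEs continuously does not lapse on an infusion day, and a rule that treatment must be withheld for toxicity presupposes that toxicity is known. The note speaks of the recording interval, so it may only space out form completion. The relaxation is optional, conditioned on clinical appropriateness, and late. The patient still attends every 3 weeks for vital signs, laboratory review, medication review and infusion. New antidiarrheals or steroids could surface in the medication review, and a Grade 3 event is unlikely to pass unnoticed. For Grade 2 immune-related events in general, Table 4 only permits withholding.

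Much of this stands, and it limits the point. What remains is mainly Grade 2 diarrhea or colitis, for which Table 3 does require a hold, in a patient who does not mention it and is not asked.

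The recording-only reading is possible, but then the mark on the AE review row is misplaced, and 6-weekly recording sits badly with Section 10.9, which wants AEs entered in real time and required data at the end of each cycle. Either reading calls for the same edit.

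A reader might infer that later infusions go ahead with no safety check. The documents do not support that, given the vital signs, laboratory and medication reviews above. Nor do they support reading the 6-week interval as the required schedule: the note only permits it.

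**Conclusion.** The point holds as a minor one. The note, applied to the AE review row, permits scheduled AE review every 6 weeks against infusions every 3 weeks, and it sits awkwardly with Sections 7.1.2.1 and 7.1.2.4. About half of the later infusions could lack a scheduled review: 5 of 10, or 13 to 14 of 27, depending on the treatment limit and the cycles skipped. These are per-patient ceilings. They assume full use of the option, a regular 21-day grid and no delays.

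How many patients this touches cannot be computed. The documents give no proportion still on treatment at week 24, no late-onset rate and no missed-event rate. With at most 30 patients, and Section 4.2.4.1 citing a median survival of 6 months or less in a poor-prognosis population, the number is probably small. That survival figure may not fit the cohort entering with stable disease.

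Some Flow Chart rows are missing from the text available, so the finding that no pre-infusion review is scheduled is limited to what can be read; the AE row itself is legible. A reader might also suspect an effect on the response-rate conclusion. There is none: the primary endpoint and the two-stage rule do not depend on the AE review interval.

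**What to change.** Delete AE recording from the double-asterisk note and remove the mark from the two AE review cells (cycles 6 and 8). The note could read: *After cycle 8, full physical examination and ECOG may be done every other cycle (every 6 weeks) where clinically appropriate. A brief AE and symptom review is done before every pembrolizumab infusion.* Align Section 7.1.2.4 so that its ECOG timing matches the note.

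This restores a 21-day review interval (at most 27 days with the dosing window) and lets the Table 3 and Table 4 holds work at each dose. It also fits the per-cycle data requirement in Section 10.9. The cost is one reworded note, two table cells and one aligned sentence, plus a short AE review at infusion visits the patient already attends. No visit is added, and sample size and analysis do not change.

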**End of Treatment = end of 2 years of treatment OR progressive disease as outlined in prior section.**

**Survival follow-up** can be done via phone if patient is not coming in for additional care

*Laboratory tests for screening or potentially a Second Treatment Course should be performed within 14 days prior to the first dose of treatment. After Cycle 1, pre-dose laboratory procedures can be conducted up to 72 hours prior to dosing.*

## **7.0 TRIAL PROCEDURES**

### **7.1 Trial Procedures**

The Trial Flow Chart - Section 6.0 summarizes the trial procedures to be performed at each visit. Individual trial procedures are described in detail below. It may be necessary to perform these procedures at unscheduled time points if deemed clinically necessary by the investigator.

Furthermore, additional evaluations/testing may be deemed necessary by the Sponsor and/or Merck/Incyte for reasons related to subject safety. In some cases, such evaluation/testing may be potentially sensitive in nature (e.g., HIV, Hepatitis C, etc.), and thus local regulations may require that additional informed consent be obtained from the subject. In these cases, such evaluations/testing will be performed in accordance with those regulations.

#### **7.1.1 Administrative Procedures**

##### **7.1.1.1 Informed Consent**

The Investigator must obtain documented consent from each potential subject prior to participating in a clinical trial.

###### **7.1.1.1.1 General Informed Consent**

Consent must be documented by the subject's dated signature or by the subject's legally acceptable representative's dated signature on a consent form along with the dated signature of the person conducting the consent discussion.

A copy of the signed and dated consent form should be given to the subject before participation in the trial.

The initial informed consent form, any subsequent revised written informed consent form and any written information provided to the subject must receive the IRB's approval/favorable opinion in advance of use. The subject or his/her legally acceptable representative should be informed in a timely manner if new information becomes available that may be relevant to the subject's willingness to continue participation in the trial. The communication of this information will be provided and documented via a revised consent form that captures the subject's dated signature or by the subject's legally acceptable representative's dated signature.

The informed consent will adhere to IRB requirements and applicable laws and regulations.

### **7.1.1.2 Inclusion/Exclusion Criteria**

All inclusion and exclusion criteria will be reviewed by the investigator or qualified designee to ensure that the subject qualifies for the trial.

### **7.1.1.3 Medical History**

A medical history will be obtained by the investigator or qualified designee. Medical history will include all active conditions, and any condition diagnosed within the prior 10 years that are considered to be clinically significant by the Investigator. Details regarding the disease for which the subject has enrolled in this study will be recorded separately and not listed as medical history.

### **7.1.1.4 Prior and Concomitant Medications Review**

#### **7.1.1.4.1 Prior Medications**

The investigator or qualified designee will review prior medication use, including any protocol-specified washout requirement, and record prior medication taken by the subject within 28 days before starting the trial. Treatment for the disease for which the subject has enrolled in this study will be recorded separately and not listed as a prior medication.

#### **7.1.1.4.2 Concomitant Medications**

The investigator or qualified designee will record medication, if any, taken by the subject during the trial. All medications related to reportable SAEs and ECIs should be recorded as defined in Section 7.2.

### **7.1.1.5 Disease Details and Treatments**

#### **7.1.1.5.1 Disease Details**

The investigator or qualified designee will obtain prior and current details regarding disease status.

#### **7.1.1.5.2 Prior Treatment Details**

The investigator or qualified designee will review all prior cancer treatments including systemic treatments, radiation and surgeries.

#### **7.1.1.5.3 Subsequent Anti-Cancer Therapy Status**

The investigator or qualified designee will review all new anti-neoplastic therapy initiated after the last dose of trial treatment. If a subject initiates a new anti-cancer therapy within 30 days after the last dose of trial treatment, the 30 day Safety Follow-up visit must occur before the first dose of the new therapy. Once new anti-cancer therapy has been initiated the subject will move into survival follow-up.

#### **7.1.1.6 Assignment of Randomization Number**

Not applicable, this is an open label, non-randomized trial

#### **7.1.1.7 Trial Compliance (Medication/Diet/Activity/Other)**

Patients are expected to follow the outlined treatment schedule, and violation of trial procedures may lead to trial discontinuation (see Section 5.8) if compliance is felt to impact treatment in a meaningful way or interpretability of data (consultation with the PI recommended).

### **7.1.2 Clinical Procedures/Assessments**

#### **7.1.2.1 Adverse Event (AE) Monitoring**

The investigator or qualified designee will assess each subject to evaluate for potential new or worsening AEs as specified in the Trial Flow Chart and more frequently if clinically indicated. Adverse experiences will be graded and recorded throughout the study and during the follow-up period according to NCI CTCAE Version 4.0. Toxicities will be characterized in terms regarding seriousness, causality, toxicity grading, and action taken with regard to trial treatment.

Please refer to section 7.2 for detailed information regarding the assessment and recording of AEs.

Safety assessments will consist of monitoring and recording all adverse events and serious adverse events, the regular monitoring of hematology, blood chemistry and urine values, regular measurement of vital signs and the performance of physical examinations.

These assessments should be performed within  $\pm 7$  days of the scheduled day of assessment except for adverse events that will be evaluated continuously through the study. Safety and tolerability will be assessed according to the NIH/NCI CTC [http://evs.nci.nih.gov/ftp1/CTCAE/CTCAE\\_4.03\\_2010-06-14\\_QuickReference\\_5x7.pdf](http://evs.nci.nih.gov/ftp1/CTCAE/CTCAE_4.03_2010-06-14_QuickReference_5x7.pdf)

Patients whose treatment is interrupted or permanently discontinued due to an adverse event or abnormal laboratory value suspected to be related to treatment must be followed at least weekly until the adverse event or abnormal laboratory resolves or returns to grade 1. If a patient requires a dose delay of >16 weeks from the intended day of the next scheduled dose, then the patient must be discontinued from the study.

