### 5.3.1 Criteria and Procedures for Treatment Interruption

In some circumstances, it may be necessary to temporarily interrupt both study treatments as a result of AEs that may have an unclear relationship to study drug. Any interruptions of > 2 weeks or for LFT abnormalities must be discussed with the medical monitor before resuming

treatment. Treatment with both study drugs should be withheld for drug-related Grade 4 hematologic toxicities, nonhematological toxicity  $\geq$  Grade 3 (including laboratory abnormalities), and severe or life-threatening AEs (see Table 3). Table 3 summarizes the dosing actions for MK-3475 and INCB024360 that must be implemented with the indicated related AEs. Additional information related to dose changes for INCB024360 and MK-3475 can be found in subsequent Sections.

Except in cases of emergency, it is recommended that the investigator consult with the sponsor's medical monitor (or other representative of the sponsor) before temporarily interrupting therapy for reasons other than Protocol-mandated medication hold. Additionally, the investigator must notify the sponsor's medical monitor and study project manager via email before restarting study drug that was temporarily interrupted because of an AE.

Dosing interruptions are permitted in the case of medical / surgical events or logistical reasons not related to study therapy (e.g, elective surgery, unrelated medical events, subject vacation, and/or holidays). Subjects should be placed back on study therapy within 3 weeks of the scheduled interruption, unless otherwise discussed with the sponsor. The reason for interruption should be documented in the subject's study record.

In case toxicity does not resolve to Grade 0 to 1 within 12 weeks after last infusion of MK-3475, study treatment should be discontinued after consultation with the sponsor. With investigator and sponsor agreement, subjects with a laboratory AE still at Grade 2 after 12 weeks may continue treatment in the study only if asymptomatic and controlled. For information on the management of irAEs, see below/next sections.

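### Tables 3 and 4 give different stopping rules for immune-related Grade 3 liver events and for steroid taper after Grade 3 colitis, and no sentence says which table governs

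*Combined protocol and SAP*

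**What the plan says.** Table 3 sets dose actions for drug-related adverse events by toxicity. Its AST/ALT/bilirubin row holds both drugs at Grade 2 and permanently discontinues both at Grades 3 and 4. Its diarrhea/colitis row holds both drugs at Grades 2 and 3. It then discontinues if the toxicity is unresolved 12 weeks after the last dose, or on "inability to reduce corticosteroid to 10 mg or less of prednisone or equivalent per day within 12 weeks".

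Table 4 sets actions for immune-related events by grade, whatever the organ. Its Grade 3 row tells the investigator to "withhold MK-3475 and INCB024360". It makes the stop permanent if the event recurs, if it is life-threatening, or under this steroid rule: "Discontinue if unable to reduce corticosteroid dose to < 10 mg/day prednisone equivalent within 12 weeks of toxicity".

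Section 5.3.1 directs that both drugs be withheld for non-hematological toxicity of Grade 3 or worse, laboratory abnormalities included. It points to Table 3 in the same sentence and then describes the Table 3 actions as obligatory. It adds a time limit, to be applied once the sponsor has been consulted: "In case toxicity does not resolve to Grade 0 to 1 within 12 weeks after last infusion of MK-3475, study treatment should be discontinued". It also allows an exception, by agreement of investigator and sponsor: "subjects with a laboratory AE still at Grade 2 after 12 weeks may continue treatment in the study only if asymptomatic and controlled".

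Section 7.1.2.1 closes its paragraph on interruptions for adverse events with a separate limit: a patient who needs a "dose delay of >16 weeks from the intended day of the next scheduled dose" leaves the study.

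**The concern.** An immune-mediated hepatitis is both a drug-related event (Table 3) and an immune-related event (Table 4), and so is an immune-mediated colitis. For such events both tables apply, and on two items they do not agree. On the liver item, one outcome is a permanent stop and the other is a hold with a possible restart.

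The main stake is re-exposure after serious immune toxicity. There is also a narrow route into the efficacy analysis. Section 5.10 replaces patients who receive no dose or one dose, and limits the primary analysis to those with two or more pembrolizumab doses. If a Grade 3 liver event follows the first infusion, Table 3 leads to replacement, while Table 4 leaves open a second dose and inclusion. Under Section 8.1 each cohort has at most 15 patients and two responses reject the null hypothesis, so the set of evaluable patients should not depend on which table was consulted.

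**Working it through.** The plan states no figure to reproduce here. The check is a side-by-side reading, followed by date arithmetic.

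**Step 1. Events covered by both tables.**

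| Event | Table 3 | Table 4 | Same action? |
|---|---|---|---|
| Immune-related Grade 3 AST, ALT or bilirubin | Permanent stop, both drugs | Withhold both; permanent stop only on taper failure, recurrence or a life-threatening event | No |
| Grade 3 colitis, prednisone at exactly 10 mg/day at the limit | Passes (10 ≤ 10) | Fails (10 is not < 10) | No |
| Grade 3 colitis, below 10 mg/day | Passes | Passes | Yes |
| Grade 3 colitis, above 10 mg/day | Fails | Fails | Yes |

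The liver conflict affects every immune-related Grade 3 event in that row. The steroid conflict affects one dose value only.

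**Step 2. The 12-week clock for colitis.** Table 3 counts resolution from the last dose, and its steroid clause names no starting point of its own. Table 4 counts the taper from the toxicity. Suppose the Table 3 steroid clause shares the last-dose clock, and onset is *d* weeks after the last infusion. Table 3 then expires at week 12 and Table 4 at week 12 + *d*. For onset within one 3-week cycle, *d* runs from 0 to 3, so the two clocks differ by 0 to 3 weeks. This range is an illustration that rests on those two assumptions.

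**Step 3. The 16-week limit on the same clock as Section 5.3.1.** The flow chart footnote in Section 6.1 gives "Treatment cycle length = 21 days", or 3 weeks.

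- Section 7.1.2.1 limit, from the last infusion: 3 + 16 = 19 weeks (19 × 7 = 133 days).
- Section 5.3.1 limit, as a delay from the next due dose: 12 − 3 = 9 weeks.
- Distance between the limits: 19 − 12 = 7 weeks, or 7 / 3 ≈ 2.3 cycles.

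The two limits also differ in trigger and consequence. Section 5.3.1 acts on unresolved toxicity and ends study treatment. Section 7.1.2.1 acts on the length of the delay and ends study participation.

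**Step 4. Search for a rule of precedence.** Sections 5.3 and 5.3.1 send the reader to Table 3, and 5.3.1 makes its actions binding. The title of Table 4 presents it as a general approach. Against that, Table 4 never refers to Table 3, and it carries event-specific instructions of its own (Grade 3 rash). Other cross-references do not help: Section 5.7.1 sends the reader to 5.2.1 for dose modification, but 5.2.1 is Dose Selection. Section 5.9 cites 5.2.1.2, which does not appear in the text.

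**The case against.** The strongest reply is that Table 3 already governs: it is specific and declared binding, while Table 4 is general. This is a fair reading and probably the intended one. It also answers an inference that a reader might draw, that Section 5.3.1 itself contradicts Table 3 on liver events by saying to withhold. That sentence points to Table 3, so it does not support a separate conflict. But the ranking of Table 3 over Table 4 has to be inferred. Section 5.3.1 does not follow Table 3 consistently either: its exception for Grade 2 laboratory events departs from the Grade 2 liver row, which discontinues when the event is unresolved at 12 weeks.

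A second reply is that no investigator decides alone. Under 5.3.1, interruptions for liver-test abnormalities, or longer than 2 weeks, must be discussed with the medical monitor before treatment resumes. Under 5.3.2, immune-related events of Grade 2 or higher go to the PI at once. Sections 10.2 and 10.6 describe a single-center study. It would therefore be too strong to infer that investigators could act in opposite ways with nothing to check them. Consultation lowers that risk, but it does not tell those consulted which rule applies.

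A third reply concerns the 16-week sentence. A reader might take it as permission to keep a patient with unresolved toxicity on treatment until week 19. The text does not say that. A patient stopped at 12 weeks never reaches the later limit, so both rules can be obeyed. The later limit also has possible uses: the Grade 2 laboratory exception, and the Table 3 diabetes/hyperglycemia row, which states no 12-week limit. The 7 weeks therefore separate two different rules. What stands is that no cross-reference connects them.

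**Conclusion.** The conflict between Tables 3 and 4 is real on two items. For immune-related Grade 3 liver events the difference is a permanent stop against a possible restart. For Grade 3 colitis it is confined to patients at exactly 10 mg/day, plus a difference in where the 12 weeks start. Table 3 probably governs, but the protocol does not say so. The 16-week limit is a secondary point: it is compatible with the 12-week rules if read as an outer limit, and its relation to them should be stated.

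A reader might also infer that reported discontinuation rates would be distorted. Section 8.1 plans toxicity tables by type and severity with incidence rates, and names no discontinuation rate, so that inference is not supported. The effect on the primary analysis is limited to events after the first infusion, and the documents give no frequency from which to size it.

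The conclusion assumes that the events are both drug-related and immune-related. It uses only table rows that are legible in the text and relies on no row being absent. The point should be corrected, but it leaves the two-stage design and its error rates untouched.

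**What to change.** Reconcile Tables 3 and 4 so that each hepatic grade carries one action, and the steroid taper has one threshold and one 12-week clock with a named starting point. Add a sentence stating which table governs when an event falls under both. In Section 7.1.2.1, cross-reference the 16-week limit to the 12-week rules and say whether it is an outer limit on delays for any reason.

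The actions, threshold and durations are for the sponsor to decide; nothing here favors one over another. The cost is protocol wording only, with no change to sample size, visits or analysis.
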